10.8.1.3 Listing of Adverse Events

The following listings will be presented for patients in the SAF:

- AEs
- TEAEs leading to premature withdrawal of study treatment
- TEAEs leading to study treatment interruption
- Treatment Related TEAEs
- Serious AEs
- Fatal AEs.

10.8.2 Laboratory Assessments

A listing will be provided for female patients in the SAF displaying the results of pregnancy test assessments during study as documented on the eCRF Page 'Urine Pregnancy Test'.

10.8.3 BCDVA assessments for Safety Evaluation

The incidences of Substantial Decrease of Visual Acuity during Treatment and Substantial Decrease of Visual Acuity during Follow-Up will be summarized by Primary/Secondary Eye for the SAF. Each occurrence of a Substantial Decrease will be flagged in the corresponding listing describing BCDVA assessments for the ITT.

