6.1 Analysis Sets

Evaluability for all patients and visits will be determined during a Blind Data Review Meeting, which will take place before unmasking the study for the main objective analysis (i.e. comprising data up to Week 12 Visit).

The Total Set (TOT) will include all patients that have signed informed consent.

The Intent-to-treat Set (ITT) will include all randomized patients and will be used for all exploratory efficacy analyses. All analyses based on the ITT will be summarized by the treatment randomized.

The Safety Set (SAF) will include all randomized patients who receive at least one dose of study medication. This safety population will be used in the analysis of all safety endpoints.

A subset of all patients in the SAF, who entered the Follow-Up Period (SAF-F), will be used in addition to present event-type analyses of the Follow-Up Period. A patient will therefore be considered as entering the Follow-Up Period, if he/she did not terminated the study at or before the Week 8 visit.

All analyses based on the SAF and SAF-F will be summarized by the treatment received.

For the study, both eyes are under investigation. For each patient, a Primary (Study) Eye and a corresponding Secondary Eye will be defined during a Blind Data Review Meeting (BDRM) to enable a patient based presentation of statistical analyses.

For each patient, an eye will be considered as Primary Eye, if

- the eye was treated and
- the investigator considered this eye as qualifying eye.

If both eyes are considered as qualifying eye, the right eye will be chosen.

The other eye will then be considered as Secondary Eye, if the eye was treated. If the other eye was not treated with study medication, no Secondary Eye will be assigned for this patient.

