A similar derivation will be performed for the incidence of Substantial Worsening of Visual Acuity during Follow-up Period considering all Assessments after Week 8 and Last Study Visit during the Follow-Up Period.

It needs to be noted that a Substantial Worsening of Visual Acuity as defined here will not necessarily implies an adverse event of special interest (AESI) or an USPON, as this definition is addressing a general worsening compared to start of study, whereas AESI and USPON are considering substantial changes from the last observed visit.

[figure not shown]
Changes in Visual field using Perimetry

Visual fields will be evaluated using static (Humphrey) perimetry and results are on the eCRF pages ‘Humphrey Visual Field Monitoring’ and ‘Humphrey Visual Field’. Two perimetries will be performed on different days for a total of 3 before initiating treatment and these will be reported as Baseline assessments. During treatment 3 assessments will be performed within 4 weeks. During follow up 3 perimetries will be performed within 4 weeks.

Humphrey Visual Field testing will be performed using SITA Standard. If a patient has a low vision and cannot perform the test via SITA Standard, the test is performed with the FASTPAC Standard. On the eCRF it is recorded which test type has been used.

All HVF assessments will be assigned to the respective study period according to the following rules:

- Screening Period: Date/Time of HVF assessment will be before Date/Time of First Study drug administration as documented on eCRF Page ‘Administration of Study Drug’
- Treatment Period: Date/Time of HVF assessment on/after Date/Time of First Study Drug Administration (as documented on eCRF Page ‘Administration of Study Drug’ and on/before Date of Week 8 Visit. If a patient did not perform a Week 8 Visit, all assessments after first Study Drug Intake will be assigned to the Treatment Period.

- Follow-up Period: Date/Time of HVF assessment after Date of Week 8 Visit.

Based on this assignment, the occurrence of USPON assessed via HVF will be determined.

Electroretinography (ERG)

A full field and pattern ERG will be performed according to international standards. On the eCRF page 'Electroretinography' only the PhNR result will be recorded in format 5.2 and used for statistical analysis.

For PhNR, the change from baseline will be calculated as differences for Week 8, Week 12 and Week 32 Visits.

Optical Coherence Tomography (OCT)

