8.1 General Methods

For the study, both eyes are under investigation. For analysis purposes all eye-related assessments will be displayed separately by Primary/Secondary Eye. Untreated eyes will not be considered for analysis and be listed only indicated with 'Untreated'.

For continuous variables, the mean, standard deviation, minimum, median and maximum will be presented by treatment group, together with the total number of observations and the number of missing and non-missing values. Unless otherwise specified minimum and maximum values will be reported to the same number of decimal places as the recorded measurements, mean and median are reported to one more decimal place and standard deviation one additional decimal place more than the mean.

For categorical variables, absolute and relative frequencies will be reported by treatment group. Relative frequencies will be based on all observations and reported as a percentages to one decimal place. Unless otherwise specified, percentages will be based on the number of patients with data in the considered analysis set and will not be calculated for missing categories.

Incidences over a specific time interval like adverse events, medical history and concomitant medication will be reported on a patient basis. The percentages will be calculated using the number of patients in the treatment group for the considered analysis set as denominator. For the presentation of incidences during the Follow-Up Period, the SAF-F set will be used, which results in a reduction of the denominator to the number of patients in the SAF, who have entered the Follow-Up Period.

All hypotheses will be tested at a 5% level of significance using a two-sided test.

P-values will be rounded to three decimal places. If a p-value is less than 0.001 it will be reported as "<0.001." If a p-value is greater than 0.999 it will be reported as ">0.999.

Statistical significance will be declared if the rounded p-value will be less than 0.050 unless stated otherwise. Two-sided 95% confidence intervals of the differences between the treatment groups will be calculated as indicated in sections 8.2 and 8.3.

Post-Text TLFs will be provided in collated electronic MS Word .rtf files (i.e. table columns and rows appear as free text instead of MS Word Table format).

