10.8 Adverse Events and Further Safety Assessments

10.8.1 Adverse Events

10.8.1.1 Brief Summary of Adverse Events

An overview summary will be provided for the SAF by presenting of events as well as number and percentages of affected patients for AEs, TEAEs, TEAEs in the Treatment Period, TEAEs in the Follow-Up Period, TEAEs leading to Premature Withdrawal of Study Treatment, TEAEs leading to Study Discontinuation, Treatment Related TEAEs, Serious AEs, Serious TEAEs, Treatment Related Serious TEAEs Fatal AEs, AESIs, TEAEs by severity, TEAEs in the Treatment Period by severity, TEAEs in the Follow-Up Period by severity, TEAEs by age category, TEAEs in the Treatment Period by age category, TEAEs in the Follow-Up Period by age category.

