10.8.1.2 Display of Adverse Events

Adverse event descriptive tables will be summarized separately for each study treatment and overall.

They will be summarized on a per-patient basis (i.e. if a patient reported the same event repeatedly the event will be counted only once at the specific level of display). Absolute counts (n) and percentages (%) will be presented for the number of patients with at least one adverse event, and per SOC and per PT within SOC, for the SAF. Percentages will be based on the number of patients in the population. In addition, number of events will be provided.

Descriptive tables will be ordered by descending frequency of the overall number of patients within each SOC regardless of treatment group, and then ordered within each SOC by the overall number of patients within each PT regardless of treatment group. In the event of equal frequencies tables will be ordered by active treatment frequency and then alphabetically.

The following tables will be provided:

- AEs for the SAF
- TEAEs for the SAF
- Treatment related TEAEs for the SAF
- TEAEs leading to premature withdrawal of Study Treatment for the SAF
- TEAEs leading to study discontinuation for the SAF
- Serious TEAEs for the SAF
- TEAEs by severity for the SAF
- TEAEs by age category ('≤ 65 years' vs '>65 years') for the SAF
- TEAEs in the Treatment Period for the SAF
- TEAEs in the Treatment Period by severity for the SAF
- TEAEs in the Treatment Period by age category ('≤ 65 years' vs '>65 years') for the SAF
- TEAEs in the Follow-Up Period for the SAF-F
- TEAEs in the Follow-Up Period by severity for the SAF-F
- TEAEs in the Follow-Up Period by age category ('≤ 65 years' vs '>65 years') for the SAF-F

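### SAP 8.1 puts follow-up incidences on the SAF-F, but the follow-up vision-loss rows and the follow-up rows of the adverse-event overview are assigned to the SAF

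*SAP*

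**What the plan says.** SAP 6.1 defines the SAF-F as the part of the Safety Set (SAF) that entered follow-up. A patient counts as having entered "if he/she did not terminated the study at or before the Week 8 visit". The set "will be used in addition to present event-type analyses of the Follow-Up Period".

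SAP 8.1 then sets the denominators. For incidences over a time interval: "The percentages will be calculated using the number of patients in the treatment group for the considered analysis set as denominator". For follow-up in particular: "For the presentation of incidences during the Follow-Up Period, the SAF-F set will be used, which results in a reduction of the denominator". No exception is stated.

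The sections that specify the output assign sets as follows:

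- **Follow-up vision loss.** SAP 7.2.9 defines it as the "incidence of Substantial Worsening of Visual Acuity during Follow-up Period considering all Assessments after Week 8". SAP 10.8.3 says "Substantial Decrease of Visual Acuity during Follow-Up will be summarized by Primary/Secondary Eye for the SAF". Table 14.3.2-1.1 in Section 12 is labelled SAF.
- **Adverse-event overview.** SAP 10.8.1.1 says "An overview summary will be provided for the SAF by presenting of events as well as number and percentages of affected patients", and its rows include follow-up TEAEs in total, by severity and by age category. Table 14.3.1-01.1 is labelled SAF.
- **Dedicated follow-up TEAE tables.** SAP 10.8.1.2 lists "TEAEs in the Follow-Up Period for the SAF-F", with versions by severity and by age. Tables 14.3.1-13.1, 14.1 and 15.1 are labelled SAF-F.

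**The concern.** A treated patient who leaves the study by Week 8 has no later visits at which a follow-up event could be seen, yet stays in the SAF denominator. SAP 8.1 removes such patients from follow-up incidences, and two of the tables that present those incidences do not.

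Two consequences follow, and they differ. For follow-up TEAEs, the overview and the dedicated tables can print different percentages for the same quantity in one report. For follow-up vision loss there is only one table, on the set that 8.1 does not call for, so its percentage can be lower than the rule intends.

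Safety and tolerability are the primary objective. SAP 8.2 plans no inference for the primary safety outcomes, and none is specified for these two tables, so readers will rely on the printed percentages. Section 12 marks all the tables concerned for repetition in the final analysis, so a mismatch would recur in the addendum to the study report.

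**Working it through.** The plan gives no figure to reproduce. Protocol 11.4 states that no formal sample size calculation was done, and neither document gives a dropout or event rate. The check is a comparison of denominators.

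**Inputs from the documents.** Planned arm sizes are 40 rhNGF and 20 vehicle (protocol synopsis), which agrees with 60 split 2:1.

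**Assumptions.** Every randomized patient is treated, so the SAF has 40 and 20. The share of an arm leaving the study by Week 8, d, is varied from 0 to 20%. The event counts are illustrative. All counted events fall in patients who entered follow-up, so the numerator is the same in both sets.

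**Formula.** With x affected patients and N in the SAF, the SAF-F has N(1 - d). The SAF rate is x/N and the SAF-F rate is x/[N(1 - d)]. So the SAF rate equals the SAF-F rate times (1 - d), and the relative understatement is d.

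**rhNGF arm, x = 4:**

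| d | SAF | SAF-F |
|---|---|---|
| 0% | 4/40 = 10.0% | 4/40 = 10.0% |
| 5% | 4/40 = 10.0% | 4/38 = 10.5% |
| 10% | 4/40 = 10.0% | 4/36 = 11.1% |
| 15% | 4/40 = 10.0% | 4/34 = 11.8% |
| 20% | 4/40 = 10.0% | 4/32 = 12.5% |

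The largest gap is 12.5 - 10.0 = 2.5 percentage points. The vehicle arm with x = 2 gives the same percentages: 2/20 = 10.0% on the SAF throughout, and 2/18 = 11.1% on the SAF-F at d = 10%.

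**Unequal exit.** Suppose 8 of 40 rhNGF and 1 of 20 vehicle patients leave by Week 8, with 4 and 2 events:

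- SAF: 4/40 = 10.0% versus 2/20 = 10.0%, difference 0.0 points.
- SAF-F: 4/32 = 12.5% versus 2/19 = 10.5%, difference 2.0 points.

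With equal exit (4 of 40 and 2 of 20), both sets show no difference: 10.0% versus 10.0%, and 11.1% versus 11.1%.

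**Numerator.** SAP 7.2.10 identifies a follow-up TEAE by a box on the adverse-event form. An event ticked as follow-up for an early leaver would be counted in the SAF and not in the SAF-F. Numerator and denominator therefore both have to be restricted.

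**The case against.** The strongest reply is that this is labelling only. Both tables mix treatment-period and follow-up rows, the SAF-F is a subset of the SAF, and a single table label would naturally name the wider set. A programmer who applies 8.1 row by row would produce the right denominators. The mock shells are in a separate document and may say so. What stands is that the wrong percentages are a consequence of the labels as written, not a certainty. But nothing in the SAP gives those rows a different N, and SAP 5.3 has output checked against the SAP and cross-checked with other tables, so the specification has to agree with itself.

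Second, SAP 6.1 assigns the SAF to all safety endpoints and uses the SAF-F additionally for event-type analyses, and SAP 9.1 describes event-type data as adverse events and concomitant medication, naming visual acuity separately. On 6.1 alone, the SAF is defensible for vision loss. But the rule in 8.1 covers follow-up incidences, and 7.2.9 calls this variable one. No additional SAF-F table is planned for it.

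Third, 8.1 bases percentages for categorical variables on patients with data, which would drop early leavers anyway. However, 8.1 gives interval incidences their own denominator, all patients of the arm in the set.

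Fourth, the share of all treated patients with a later event is a legitimate quantity, and the SAF-F is a post-randomization subset. Both are true, but the SAP made its choice in 8.1.

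Finally, readers can partly recompute: the adverse-event tables show counts, and each substantial decrease in acuity is flagged in a listing.

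**Conclusion.** The inconsistency is in the text and should be resolved. Its effect is conditional: it needs at least one treated patient to leave the study at or before Week 8. It is also small, a relative understatement of d and at most 2.5 points in the single-arm examples above, which rest on assumed exits and event counts.

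Stronger readings are not supported:

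- A reader might infer that vision loss is printed with two denominators. It has one, the SAF. Only follow-up TEAEs appear on both sets.
- A reader might infer that follow-up vision loss is certain to be understated. The documents give no dropout figure, and without early exits the two sets coincide.
- A reader might infer that intolerance of the drug will lower its apparent later risk. The SAF-F excludes patients who leave the study, not those who stop the drops; SAP 7.2.10 keeps treatment withdrawal and study discontinuation apart. An intolerant patient who stays in follow-up is in both sets. The supported statement is that unequal study exit between arms could distort the descriptive comparison.
- A reader might infer that a test is biased. No inferential test is affected.

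**What to change.** In SAP 10.8.3 and Table 14.3.2-1.1, use the SAF-F for numerator and denominator of the follow-up rows and print its N. For the Secondary Eye, count only SAF-F patients with a treated Secondary Eye. In SAP 10.8.1.1 and Table 14.3.1-01.1, do the same for every follow-up row: total, by severity and by age. Keep the treatment-period rows on the SAF. Show both sets in the Section 12 entries for these tables, so that they agree with 8.1 and with Tables 14.3.1-13.1 to 15.1.

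The cost is a wording change and a denominator change in two tables; the SAF-F is already defined and used in three others. The downside is that some follow-up percentages become slightly higher.

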10.8.4 External Ocular Examination

All evaluations of the motility of extraocular muscle Right and Up, Right, Right and Down, Left and Up, Left, Left and Down will be summarized descriptively by treatment group and study visit for the Primary Eye as well as the Secondary Eye. This analysis will be performed on the SAF. In addition, a shift table will be provided displaying the status of all scheduled Post-Baseline Visits in relation to the Baseline status. The percentages are based on the number of SAF patients in the respective baseline stratum of considered treatment group. These data will also be listed.

[figure not shown]
Incidences of proven eyelid deformity/abnormality, abnormal motor function of eyelids, corneal exposure in case of closed eyelid, proven punctal occlusion, punctal plugs, thermal or surgical occlusion or other punctal occlusion will be presented by treatment group and study visit for the Primary Eye as well as for the Secondary Eye. In addition, a shift table (Presence, Absence of considered abnormality) will be provided displaying the status of all scheduled Post-Baseline visits in relation to the Baseline status.

Incidences will be calculated as number and percentages of affected patients in respective treatment groups of the SAF. The percentages in the shift tables are based on the number of SAF patients in the respective baseline stratum of considered treatment group. The analysis will be performed on the SAF. Moreover, these data will be listed.

10.8.5 Slit Lamp Examination

All grading assessments of different eye structure (excluding assessment for other structures) will be summarized descriptively by treatment group and study visit for the Primary Eye as well as the Secondary Eye. In addition, a shift table will be provided displaying the status of all scheduled post-baseline visits in relation to the baseline status. The percentages are based on the number of SAF patients in the respective baseline stratum of considered treatment group. These analyses will be performed on the SAF.

All data recorded on the eCRF page 'Slit Lamp Examination (Biomicroscopy)' will be listed for the SAF.

10.8.6 Intraocular Pressure

[figure not shown]
Intraocular Pressure is summarized for the SAF by Primary/Secondary Eye for each treatment group at all visits as well as changes from baseline at all post-baseline visits.

A listing will present all documented assessments of intraocular pressure as well as the respective changes from baseline.

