For non-sexually active females, abstinence may be regarded as an adequate method of birth control; however, if the patient becomes heterosexually active during the study treatment period, she must agree to use adequate birth control methods as defined above for the remainder of the study treatment period.

Pregnancy should be avoided in patients or partners during the first month after completing the treatment with the Investigational Product.

| | |
|-----------------------------|--|
| Assessments: | Safety 
 • Adverse events • Best corrected distance visual acuity (BCDVA) • Intraocular pressure (IOP) • Slit lamp examination (SLE) • External ocular examination • Humphrey Visual Field 24-2 or 10-2 • Dilated fundus ophthalmoscopy • Ocular Coherence Tomography (OCT) • Mitochondrial redox potential • Electroretinogram (ERG) • Ocular tolerability using visual analogue scale (VAS) |
| Endpoints | Safety Endpoints: Safety will be assessed by the following outcomes (occurrence of these outcomes does not necessarily require cessation of therapy): 
 • Unexpectedly severe progression of optic neuropathy as measured by central vision loss, by visual field testing, or by examination of the optic nerve. • Intolerance or allergy to the drug. • Adverse events affecting ocular function or eye pressure, which differ from those expected in the course of glaucoma, which are thought to be potentially related to the drug. • Local or systemic toxicities considered serious adverse events that are potentially related to the drug. Elevation of intraocular pressure, although not seen previously in human use and not expected in this population, will be considered for cessation of therapy in patients with glaucoma. Data on all adverse events will be collected regardless of severity or potential relationship to the drug. Tolerability will be assessed through a Visual Analog Scale (VAS) |
| Sample size: | As the objectives of this study are to evaluate the safety and explore the biological effects of a single rhNGF dosage, sample size was calculated based on clinical feasibility and no formal sample size calculation has been performed. Proposed sample size is of 60 patients adequate to make appropriate estimation of study variables. |

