11.5.4. Safety Analysis

Safety variables will be presented for the Safety population.

The primary safety endpoint in this study is Adverse Events (AEs). AEs will be recorded at the scheduled study visits and may also be recorded at any unscheduled visit that occurs during the study.

AEs will be presented, by treatment group, in terms of the incidence, severity and relationship to the study drug, overall and by SOC (System Organ Class) and preferred term. Serious AEs (SAEs) will be presented in the same way. All adverse events will be reported by MedDRA preferred term.

The following adverse event summary tables and listings will be provided:

Tables:

- Frequency and Incidence of Subjects with Adverse Events
- Frequency and Incidence of Subjects Discontinued Due to Adverse Events
- Frequency and Incidence of Subjects with Serious Adverse Events
- Adverse Events by Coded Adverse Event and SOC
- Overall Frequency and Incidence of Adverse Events
- Overall Frequency and Incidence of Adverse Events by Severity
- Overall Frequency and Incidence of Treatment-Related Adverse Events
- Overall Frequency and Incidence of Adverse Events Occurring at Rates Greater Than or Equal to 1.0%
- Overall Frequency and Incidence of Adverse Events by Age

Listings:

- Concomitant Diseases and Medications for Subjects with Adverse Events by Investigator and by Subject
- Coded and Descriptive Terms of Adverse Events by Investigator and by Subject
- Deaths, Other Serious or Clinically Significant Adverse Events
- Adverse Events by Investigator and by Subject

In addition to reporting of adverse events for any untoward (unfavorable and unintended) medical occurrences, adverse events will also be reported for any clinically relevant change from baseline in any assessment evaluated during the study, based upon an assessment by the Investigator.

Ocular tolerability as measured by the VAS will be analyzed by means of analysis of variance, including terms for treatment, time, and treatment by time interaction.

Best corrected distance visual acuity, external ocular examination, slit lamp examination, intraocular pressure, and dilated fundus ophthalmoscopy, will be presented with the appropriate descriptive statistics and shift tables will be used to present shifts from before and after treatment at each recording time points.

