7.1 Definition of Time Points

The study consists of 7 scheduled clinical evaluation visits: Screening Visit, Baseline Visit (Therapy Initiation), Week 1, Week 4, Week 8, Week 12 and Week 32 Visit. Week 1 Visit has a window of ± 2 days, Week 4 Visit has a window of ± 4 days, while Week 8, 12, 32 Visits have a window of ± 7 days, at the discretion of the investigator, required procedures for a scheduled visit may be performed over 2 consecutive days.

If a patient returns to the clinic prior to their next scheduled study visit for assessment of an adverse event, an Unscheduled Visit should be conducted. Procedures conducted at the Unscheduled Visit are at the discretion of the Investigator.

Any patient who exits early from the study must undergo all procedures outlined at Week 8 Visit if the discontinuation occurs at or before Week 8 Visit.

All assessments except event type data will be analysed according to the nominal Visit identifier on the CRF page, irrespective of meeting the time window as specified in the study plan and of having the procedures performed over 1 or 2 consecutive days.

This rule does not hold for patients, who terminate study during treatment. For these patients, the visit needs to be shifted to Week 1, Week 4 or Week 8 visit depending on the visit window specified below.

Unscheduled visits will not be considered for by-visit analyses but all collected data will be listed. Documented unscheduled visits will be labelled as “Unscheduled Visit x.01”, “Unscheduled Visit x.02”, “Unscheduled Visit y.01” etc. indicating the number of the last preceding visit plus a consecutive sequence number.

The Baseline value is generally defined as the last non-missing measurement collected or derived prior to the first Study Treatment Administration as recorded on eCRF page “Administration of Study Drug’ in variables Date/Time of Application of First Dose.

The Treatment Day of an event/assessment will be calculated relative to the First Study Treatment [defined as Variable “Date of First Dose Treatment’, recorded on “Study Drug Dosing Dates’ eCRF form].

The Treatment Day of events/assessments occurring before the First Study Treatment will be calculated as:

- Treatment Day = (Date of assessment/event - Date of First Study Treatment).

For events/assessments occurring on or after First Study Treatment Administration, Treatment Day will be calculated as:

- Treatment Day = (Date of assessment/event - Date of First Study Treatment) + 1.

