Table 14.3.1-13.1	Summary of TEAEs in the Follow-Up Period by System Organ Class and Preferred Term	SAF-F	R	Y
Table 14.3.1-14.1	Summary of TEAEs in the Follow-Up Period by Severity, System Organ Class and Preferred Term	SAF-F	R	Y
Table 14.3.1-15.1	Summary of TEAEs in the Follow-up Period by Age Category, System Organ Class and Preferred Term	SAF-F	R	Y
Table 14.3.2-1.1	Summary of Substantial Worsening of Visual Acuity	SAF	U	Y
Table 14.3.3-1.1	Summary of Motility of Extraocular Muscle	SAF	U	Y
Table 14.3.3-1.2	Shift Table for Motility of Extraocular Muscle	SAF	U	Y
Table 14.3.3-2.1	Summary of Appearance and Function of Eyelid	SAF	U	Y
Table 14.3.3-2.2	Shift Table for Appearance and Function of Eyelid	SAF	U	Y
Table 14.3.4-1.1	Summary of Slit Lamp Examination	SAF	U	Y
Table 14.3.4-1.2	Shift Table for Slit Lamp Examination	SAF	U	Y
Table 14.3.5-1.1	Summary of Intraocular Pressure	SAF	U	Y
Table 14.3.5-1.2	Summary of Changes from Baseline in Intraocular Pressure	SAF	U	Y
Table 14.3.6-1.1	Summary of Dilated Fundus Ophthalmology	SAF	U	Y
Table 14.3.6-1.2	Shift Table for Dilated Fundus Ophthalmology	SAF	U	Y
Listings				
Listing 16.1.7-1.1	Randomized Allocation to Treatment and Assigned Kit Numbers	ITT	U	N
Listing 16.2.1-1.1	Listing of Study Completion, Unmasking and Duration of Study Periods	TOT	U	Y
Listing 16.2.2-1.1	Listing of Protocol Deviations	ITT	U	Y
Listing 16.2.2-1.2	Listing of Inclusion Criteria	ITT	U	N
Listing 16.2.2-1.3	Listing of Exclusion Criteria	ITT	U	N
Listing 16.2.3-1.1	Listing of Allocation to Analysis Sets	TOT	U	N
Listing 16.2.4-1.1	Listing of Demographic Data	ITT	U	N
Listing 16.2.4-2.1	Listing of Glaucoma History	ITT	U	N
Listing 16.2.4-3.1	Listing of Medical History	ITT	U	N
Listing 16.2.4-3.2	Listing of Surgical History	ITT	U	N
Listing 16.2.4-4.1	Listing of Prior and Concomitant Medication	ITT	U	Y
Listing 16.2.5-1.1	Listing of Exposure, Compliance and Days on Study Treatment	ITT	U	N
Listing 16.2.5-1.2	Listing of First Study Drug Administration	ITT	U	N

TLF number	Title	Analysis Set	U/R	SR
Listing 16.2.6-1.1	Listing of Primary Safety Outcomes	SAF	U	N
Listing 16.2.6-2.1	Listing of VAS Ocular Tolerability Scores	SAF	U	N
Listing 16.2.7-1.1	Listing of BCDVA Assessments	ITT	U	Y
Listing 16.2.7-1.2	Listing of BCDVA Scores, Snellen Equivalent and LogMAR	ITT	U	Y
Listing 16.2.8-1.1	Listing of HVF Assessments	ITT	U	Y
Listing 16.2.9-1.1	Listing of ERG Assessments	ITT	U	Y
Listing 16.2.10-1.1	Listing of OCT Assessments – Part I	ITT	U	Y

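### The SAP drops the IOP and BCDVA shift tables promised in the protocol without saying so, and no planned table counts patients by size of IOP change

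*SAP*

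**What the plan says.** Protocol 11.5.4 lists five examinations in one sentence: "Best corrected distance visual acuity, external ocular examination, slit lamp examination, intraocular pressure, and dilated fundus ophthalmoscopy". For all five it promises descriptive statistics, and it adds that "shift tables will be used to present shifts from before and after treatment at each recording time points". Protocol 11.5.1 says that changes to the planned analyses are to be reported and justified in the SAP.

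On IOP, SAP 10.8.6 states: "Intraocular Pressure is summarized for the SAF by Primary/Secondary Eye for each treatment group at all visits as well as changes from baseline". The table list in SAP section 12 has two IOP tables, 14.3.5-1.1 for the values and 14.3.5-1.2, titled "Summary of Changes from Baseline in Intraocular Pressure". SAP 8.1 fixes their content: "For continuous variables, the mean, standard deviation, minimum, median and maximum will be presented by treatment group". A listing shows every IOP value and its change from baseline. SAP 7.1 sets the rule for other visits: "Unscheduled visits will not be considered for by-visit analyses but all collected data will be listed".

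The protocol synopsis singles out pressure under the safety endpoints: "Elevation of intraocular pressure, although not seen previously in human use and not expected in this population, will be considered for cessation of therapy".

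**The concern.** The primary objective is safety and tolerability, in glaucoma patients. Protocol section 4 explains that the trial was set up as phase I because there were no data on rhNGF in patients with a history of raised pressure. A reader of the report will want to know how many patients in each arm had a pressure rise, and from what starting level. A shift table answers that. The protocol promised one, the SAP leaves it out, and nothing in the SAP shows that this was a decision rather than an oversight.

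Unscheduled visits add to this. They are held to assess an adverse event, and an IOP reading taken only at such a visit enters neither IOP table. The SAP handles acuity differently: unscheduled assessments count towards both Substantial Worsening (7.2.9) and unexpected severe progression of optic neuropathy, USPON (7.2.7).

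**Working it through.** **Step 1. Compare the promise with the plan.** The plan gives no power, SD or IOP threshold to reproduce, so the main check is a comparison of texts.

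| Variable named in protocol 11.5.4 | Shift table in the SAP? |
|---|---|
| External ocular examination | Yes: 10.8.4, Tables 14.3.3-1.2 and 14.3.3-2.2 |
| Slit lamp | Yes: 10.8.5, Table 14.3.4-1.2 |
| Fundus ophthalmoscopy | Yes: 10.8.7, Table 14.3.6-1.2 |
| IOP | No: 10.8.6, Tables 14.3.5-1.1 and 14.3.5-1.2 only |
| BCDVA | No: 10.7.1 and 10.8.3; incidence Table 14.3.2-1.1 instead |

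SAP 3.6 lists changes for mitochondrial redox potential, ERG, visual fields, the Safety Set definition and the layout of adverse event tables. It mentions neither missing shift table.

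**Step 2. What the planned IOP tables show.** By eye, arm and scheduled visit they show the mean, SD, minimum, median and maximum of the value and of the change. They do not count patients by size of change or cross baseline with later status. With five post-baseline visits (Weeks 1, 4, 8, 12 and 32), separate maxima do not show whether one patient or several produced them.

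**Step 3. Why a maximum is not a count (illustration).** Input from the protocol: 40 rhNGF patients. Assumptions, because the documents give none: *k* patients rise by *r* = 10 mmHg, no other patient exceeds that, and the others average no change with SD *s* of 2 to 3 mmHg.

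- Mean shift: *m* = *k* × *r* / *n*. For *k* = 1, 1 × 10 / 40 = 0.25 mmHg. For *k* = 4, 4 × 10 / 40 = 1.0 mmHg.
- SD of the arm: √{[((*n* − *k*)*s*² + *k r*²)/*n* − *m*²] × *n*/(*n* − 1)}. For *k* = 1 this is 2.55 (*s* = 2) or 3.39 (*s* = 3). For *k* = 4 it is 3.59 (*s* = 2) or 4.19 (*s* = 3).
- Maximum: +10 in every case.

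The SD does not reveal the count either. One patient with *s* = 3 gives 3.39 and four patients with *s* = 2 give 3.59, and the reader does not know *s*.

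**Step 4. Is more than one case plausible?** If the true rate of such rises is 5% (assumed), P(at least 1 of 40) = 1 − 0.95⁴⁰ = 0.87, and P(at least 2 of 40) = 1 − 0.95⁴⁰ − 40 × 0.05 × 0.95³⁹ = 0.60. For true rates of 2.5% to 10%, the second probability runs from 0.26 to 0.92. The count is therefore worth having.

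**Step 5. Unscheduled readings.** SAP 10.8.6 speaks of all visits, but the general rule in 7.1 keeps unscheduled visits out of by-visit analyses. Under that rule, a rise seen only at an unscheduled visit does not reach even the printed maximum.

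**The case against.** The case for leaving the SAP alone is substantial. A reader might infer from 10.8.6 that IOP is reported only as means and that large rises would go unseen in the tables. The documents do not support this. SAP 8.1 requires the maximum and the SD, so in the illustration the change table prints +10, and all values are listed for at most 60 patients.

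A reader might also set the mean shift against a confidence interval for the arm difference. The SAP plans no inference on IOP, so that comparison sizes an analysis nobody will run.

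Nor do the documents support the inference that unscheduled visits are where a spike is most likely to be measured. IOP is taken at all seven scheduled visits, and procedures at unscheduled visits are at the investigator's discretion.

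There is also another route to a patient count. Protocol 11.5.4 and 12.2 require any clinically relevant untoward change in a study parameter to be reported as an adverse event, whatever its cause. Treatment-emergent events are then counted per patient by preferred term and arm. Potentially related events affecting eye pressure that differ from the expected course of glaucoma are also a primary safety outcome. This narrows the gap, but both counts depend on the investigator judging the change relevant and, for the second, related and unexpected. Neither is a count from the measurements.

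For acuity, Substantial Worsening has its own table and USPON, which includes an acuity component, is tabulated as well. What remains uncategorised is loss below those levels.

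**Conclusion.** The departure from the protocol is established from the text: two promised shift tables are missing and SAP 3.6 does not mention it. Its consequence is limited. The largest IOP rise at each scheduled visit will be visible. How many patients rose, and from what baseline, will not be tabulated, and a rise found only at an unscheduled visit will appear in the listing or, if reported, as an adverse event. The figures of 0.25 and 1.0 mmHg under one maximum rest on an assumed rise of 10 mmHg. They show what is lost and do not predict IOP behaviour in this trial. The acuity gap is smaller than the IOP gap. The correction should be made because it bears on the primary safety question and uses data already collected, but the omission does not undermine the safety analysis as a whole.

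**What to change.** In SAP 10.8.6 and section 12:

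- Add the promised IOP shift table by eye, arm and visit, with categories that the sponsor fixes before unmasking. The documents give no categories and none is proposed here.
- Add a table by arm of each treated eye's maximum post-baseline change in IOP, including unscheduled readings, with patient counts or a cumulative distribution. The distribution needs no cut-off. A maximum tends to grow with the number of readings, so print the number of readings per patient beside it.

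In SAP 10.8.3, add the promised BCDVA shift table, or record and justify its omission in 3.6. If the sponsor prefers not to produce the IOP shift table, the same entry in 3.6 is the minimum.

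The cost is two or three extra tables from data already in the eCRF, repeated at the final analysis as the existing IOP tables are. The one constraint is timing: categories must be settled before unmasking, and the blind data review meeting after the last Week 12 visit is the last natural occasion.
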